Disease response will be assessed by serial CAT or CT/PET imaging with or without bone marrow aspiration & biopsy (if clinically indicated) at days +100 (\pm 28 days), +180 (\pm 28 days) and +365 (\pm 28 days). Additional imaging and clinical investigations to assess disease relapse and/or progression are permitted if clinically indicated (at the discretion of treating oncologist). The standard revised response criteria (International Harmonization Project) (12) for lymphoma presented in Appendix D, will be used to assess disease response throughout the study per the Study Calendar (please see section 7).

6.6. Removal of Patients from Protocol therapy:

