6.6.2. Extraordinary medical circumstances

If, at any time, the constraints of this protocol are detrimental to the patient's health and/or the patient no longer wishes to continue protocol therapy, protocol therapy shall be discontinued. In this event:

- Notify the Study Chair.
- Document the reason(s) for discontinuation of therapy in patient records.
- Follow the patient for survival, progression, relapse, and secondary malignancies, if possible.

7. Study Parameters (Study Calendar):

7.1. Patient Study Calendar:

The table below summarizes the patient clinical assessments over the course of the study.

Study Assessment	Baseline ¹	Conditioning Phase					Day	Days Post-Transplantation												365/	730		
		-7	-6	-5	-4	-3		0	7	14	21	30	35	42	49	56	63	70	77	84	100		
Informed Consent	X																						
History & physical exam ²	X														X			X		X		X	
Vital signs ³	X	X	X	X	X	X								X			X		X		X		
Karnofsky performance status	X														X			X		X		X	
CBC, differential, & platelets	X	X	X	X	X	X								X ⁴	X ⁴	X ⁴	X ⁴	X		X		X	
Serum chemistries panel ⁵	X	X	X	X	X	X								X	X	X	X		X		X		
Infectious disease titers ⁶																							
LVEF ⁷	X																						
DLCO ⁷	X																						
Ann Arbor stage (at transplant)	X																						
Disease risk score ¹⁵ (at transplant)	X																						
CMV quantitative PCR															X	X	X	X	X	X	X	X	
Bone marrow aspirate/biopsy ^{8,13}	X																						
β-HCG serum pregnancy test ⁹	X																						
Quantitative immunoglobulins ¹⁰															X								
Peripheral blood for chimerism		X ¹¹													X			X		X		X	
Immune reconstitution panel ¹²															X			X		X		X	
CD34/CD3 cell dose infused															X								

Study Assessment	Baseline ¹	Conditioning Phase					Day	Days Post-Transplantation												365	& 730		
		-7	-6	-5	-4	-3		0	7	14	21	28	35	42	49	56	63	70	77	84	100	180	
Seizure prophylaxis		X																					
PK Sample Submission ¹⁴			X																				
PK-directed IV Busulfex dose				X	X																		
Fludarabine/Busulfex ±ATG conditioning				X	X	X	X																
HPCT infusion						X																	
ANC and platelet recovery ¹⁶																							
CT or PET/CT chest/abdomen/pelvis ¹⁷		X																			X	X	X
Acute/chronic GVHD assessment									X	X	X	X	X	X	X	X	X	X	X	X	X	X	
Toxicity assessment									X	X	X	X	X	X	X	X	X	X	X	X	X	X	
Research specimens (Voluntary) ¹³		X							X			X		X		X		X		X	X	X	

Notes

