OS and progression free survival PFS will be estimated using the Kaplan-Meier method. OS is defined as the time from transplant to death, and surviving patients will be censored at last follow-up. PFS is defined as the time from transplantation to disease progression/relapse and/or death. OS and PFS data between subgroups will be analyzed by the log-rank test. NRM is defined as death from any cause other than disease progression or relapse. Cumulative incidences of NRM and relapse will be calculated with relapse or death as a competing event, respectively [37]. Comparisons between estimates of cumulative incidence will be made by using the Gray's test. The cumulative incidence of acute or chronic GVHD will be calculated with relapse or death without GVHD as competing events [37,38]. We anticipate that a maximum of 32 patients will be accrued to the study. Descriptive statistics (i.e. means, standard deviations, 95% confidence intervals for continuous variables, and frequencies for discrete data) will be computed for all correlative laboratory parameters. Given the small sample size in this phase II trial, a total of 32 patients limits our ability to perform inferential tests.

Accrual Estimate: 32 patients.

Accrual Period: Until 12/31/2013.

Safety/Stopping Rules:

Rates of non-relapse mortality and grade III-IV acute GVHD will be monitored on 6 monthly basis. The study will be halted for review by the data safety and toxicity committee (DSTC) if any of the following criteria are met.

1. Non-relapse mortality of >40% at day 100 after transplantation.
2. Cumulative incidence of grade III-IV acute GVHD is >40% at day 100 after transplantation.

Follow-Up Period : One year to evaluate progression free survival.

10. Records to be Kept:

Particular attention should be given to the specification of which data elements should be included in the Mary Babb Randolph Cancer Center Clinical Trials Research Unit OnCore database. The investigator will maintain adequate records in the Investigator Site File to enable the conduct of the study to be fully documented. All documents related to the conduct of the study will be kept on file in a readily accessible order. This file must be safely archived after the termination of the study.

Patient data collected on Case Report Forms (CRFs) should be sent to the Network Coordinator at the CTRU by fax at [contact] according to CRF submission guidelines provided by WVU. Data will be entered into the OnCore database.

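### Does the lack of a stated censoring rule for PFS in section 9 leave the primary 1-year estimate open?

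*Combined protocol and SAP*

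**What the plan says.** Section 9 covers both endpoints with one estimator: "OS and progression free survival PFS will be estimated using the Kaplan-Meier method". It then says "OS is defined as the time from transplant to death, and surviving patients will be censored at last follow-up", and for the primary endpoint "PFS is defined as the time from transplantation to disease progression/relapse and/or death". No PFS censoring date is given there or elsewhere. The follow-up line in section 9 reads "One year to evaluate progression free survival".

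Section 6.5 sets the assessments: "Disease response will be assessed by serial CAT or CT/PET imaging" at days +100, +180 and +365, each with a window of 28 days either side. It adds that "Additional imaging and clinical investigations to assess disease relapse and/or progression are permitted if clinically indicated". For patients who stop protocol therapy, section 6.6.2 says "Follow the patient for survival, progression, relapse, and secondary malignancies, if possible".

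Section 6.1 schedules visits at 6, 12 and 24 months, and section 2.2 lists 2-year PFS as a secondary objective. In the section 7.1 calendar, the row "CT or PET/CT chest/abdomen/pelvis" appears to end in a column that covers both day 365 and day 730.

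**The concern.** OS and PFS differ in what contact with a patient proves. A telephone call shows that someone is alive; it does not show that the lymphoma has not progressed. The OS rule therefore does not carry over to PFS automatically, and many analysts would censor PFS at the last disease assessment.

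The schedule makes the choice visible. After the 6-month scan (day 208 at the latest) the next scheduled scan is the 12-month one, and its window straddles day 365. Under last-assessment censoring, a clean scan on day 345 removes the patient from the risk set before the landmark. A patient who misses that scan is censored near day 180. Under last-follow-up censoring both patients count as progression-free at one year if known to be alive without documented progression.

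This is the primary endpoint of a single-arm trial of 32 patients. If the rule is picked once the data are known, the estimate could be nudged. The dating of progression is also unwritten, and 2-year PFS has the same gap.

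**Working it through.** **Inputs from the documents.** n = 32, null 0.10 and alternative 0.35 in the power statement (section 9); 12-month scan at 365 ± 28 days (section 6.5).

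**The plan's own figure.** An exact binomial test at n = 32 that rejects for 0 or for 8 or more successes has power 0.918 at 0.35, which agrees with the stated 90%. The upper boundary is 8/32 = 25.0%, and one patient is 1/32 = 3.1 points. (Section 9 also gives a null of 0.15; that is a separate matter and does not bear on censoring.)

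**Window.** 365 − 28 = 337 and 365 + 28 = 393. The 6-month window closes at 180 + 28 = 208.

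**Early clean scans.** Take 32 patients, 21 with events and 11 event-free, 6 of the 11 last scanned clean on day 345.
- No event between day 345 and day 365: both rules give 11/32 = 34.4%.
- One event on day 360, the other 20 earlier: last follow-up gives 11/32 = 34.4%; last assessment gives 12/32 × 5/6 = 31.2%.
- Two events on day 360: 34.4% against 13/32 × 5/7 = 29.0%.

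So the rules part only when an event falls after an early clean scan and by day 365.

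**A missed 12-month scan.** A patient last scanned near day 180 counts as 1 under last follow-up and as S(365)/S(180) under last assessment. With assumed PFS falling from 30% to 15%, or from 50% to 35%, the ratio is 0.5 or 0.7. The shift is (1 − 0.5)/32 = 1.6 points or (1 − 0.7)/32 = 0.9 points per such patient.

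**Dating.** If one of the 21 events is first seen on a day-380 scan, 1-year PFS reads 12/32 = 37.5% instead of 34.4% under either censoring rule. A censoring sentence would not alter that. Dating at first documentation is the ordinary convention and settles how the case is handled.

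**Average size by simulation.** Assumptions, none from the documents: true 1-year PFS 15% or 35%; 30% of events are deaths; 30% to 80% of progressions are silent and surface clinically after a mean of 30 to 60 days; data cut at day 393.

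| 12-month scans | Mean difference between rules (points) | Trials differing by one patient or more |
|---|---|---|
| Complete, spread evenly | 0.5 to 1.0 | 6 to 9% |
| 10% missing | 1.3 to 2.1 | 13 to 25% |
| 20% missing | 2.0 to 3.5 | 25 to 47% |
| All done by day 365 | 1.8 to 5.4 | 21 to 43% |
| All done on days 366 to 393 | 0 | 0% |

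A harsher model has a constant hazard, 40% of it from death, and every progression silent until the next scheduled scan. It gives mean differences of 1.3 points (true 15%) and 2.0 (true 35%) with no missed scans, and 2.7 to 4.1 and 3.7 to 5.5 with 10% to 20% missed. It ignores the clinically prompted investigations that section 6.5 permits.

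**Later data cut.** With follow-up assumed to spread over days 393 to 1600 and a day-730 scan, the first model gives 0.2 points or less with complete scans and 0.7 or less with 20% of 12-month scans missing.

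**Against sampling error.** √(0.15 × 0.85/32) = 6.3 points; √(0.35 × 0.65/32) = 8.4 points.

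**Is another rule more accurate?** Consider a mixed rule: censor at last assessment, but treat a clean in-window 12-month scan as assessment through day 365. With no missed scans it equals last-follow-up censoring exactly. With 20% missed and a true 35%, last follow-up reads 0.3 to 1.7 points high and the mixed rule about 1 to 2 points low.

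**The case for a change.** The strongest case for a change is that the choice is free, concerns the primary endpoint, and costs one sentence to close. At the rejection boundary of 8 in 32 a single patient alters the conclusion. If every 12-month scan were done by day 365 and the data were cut at day 393, nobody would be at risk at day 365 under last-assessment censoring, and the estimate would be undefined in 37% to 50% of simulated trials. Section 9 also powers a binomial test without saying how a patient censored before day 365 enters the count.

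Part of this stands: the rule is unwritten, and writing it would be tidy. The serious cases, however, rest on conditions the documents do not indicate. Section 6.6.2 deals with patients who leave protocol therapy; it does not forecast that 10% to 20% will miss a scan. The window is symmetric about day 365, so there is no reason to expect every scan to be early. A day-393 cut for every patient is not in the plan. Accrual was open until the end of 2013 after a protocol review in June 2010, and 24-month visits and 2-year PFS are planned, so many patients would have later assessments by the time of analysis. Last assessment need not mean last scan either, since section 6.5 also allows clinical investigations.

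For 2-year PFS, section 6.5 lists no scan beyond day +365, but it defers to the calendar, whose last imaging column appears to include day 730. The column alignment in the public text is too uncertain to establish a contradiction.

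**Conclusion.** The gap is genuine, but analysts fill it sensibly. Section 9 treats OS and PFS together under Kaplan-Meier and states last follow-up for the first; carrying that to PFS, with progression dated at first documentation, is a sound reading. In the first model, with even spread and a day-393 cut, its bias is +0.2 to +0.7 points in most settings and about +1.7 at worst.

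The choice between the two ordinary rules moves 1-year PFS by 0.5 to 1.0 points on average if 12-month scans are complete and evenly spread and some progression is found clinically. That is less than a third of one patient (1.0/3.1) and at most about one eighth of the standard error (1.0/8.4). It shrinks further with later follow-up. Choosing one rule over the other is a preference, and no alternative was shown to be more accurate.

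This conclusion rests on assumed event patterns and on 12-month scans being largely complete, neither of which can be verified from the documents. If many of those scans proved to be missing or uniformly early, and the analysis were done at one year, the choice could be worth one patient or more and an analyst would naturally show both results. As the plan stands, it needs no change on this point.

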malignancies. Moreover no studies to date have prospectively explored whether Busulfex dose reduction based on high AUC could reduce NRM and pulmonary and hepatic toxicity associated with this regimen. Despite encouraging safety and efficacy of once daily IV busulfan based conditioning allogeneic HPCT, no prospective trials have been performed in patients with relapsed, refractory Hodgkin's or NHLs, to our knowledge. The current study will be a multicenter, open label phase II study of allogeneic transplantation following reduced toxicity conditioning with once daily IV Busulfex, and fludarabine for patients with chemotherapy refractory lymphoid malignancies. Median daily AUC values following once-daily Busulfex doses of $130\text{mg}/\text{m}^2$ (roughly equivalent to $3.2\text{mg}/\text{kg}$ i.v dose) range from approximately $4800\text{ }\mu\text{mol}.\text{min}$ to $5200\text{ }\mu\text{mol}.\text{min}$ [25, 26]. While it is suggested that AUC of $>6000\text{ }\mu\text{mol}.\text{min}$ are associated with negative outcomes, lower Busulfex exposure levels can potentially lead to poor donor-cell engraftment and more importantly suboptimal disease control in this high-risk group before generation of a robust graft-versus-lymphoma effect by donor stem cells. Hence we hypothesize that a strategy of therapeutic monitoring of Busulfex drug levels and dose adjust to a target AUC of $3800\text{-}5200\text{ }\mu\text{mol}.\text{min}$, will ensure uniform engraftment of donor cells, provide adequate disease control while minimizing toxicity associated with higher Busulfex exposure values.

1.7. Inclusion of Women and Minorities:

It is the policy of the Mary Babb Randolph Cancer Center to strive for gender and minority patient participation that represents the population of West Virginia in all clinical investigations. Between January 1st 2009 and December 31st 2009, 125 patients were enrolled onto Phase I/II/III trials at the Mary Babb Randolph Cancer Center. Of these patients 73% percent were female (n=92) and 2.4 percent were members of minority ethnic groups. It is anticipated that a similar or greater proportion of patients on this study will be female and/or members of ethnic minorities.

2. OBJECTIVES:

2.1. Primary Objectives:

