1. To assess 1-year progression free survival (PFS) of patients with chemotherapy refractory Hodgkin's and non-Hodgkin's lymphoma (NHL) undergoing reduced-toxicity conditioning (RTC) with once daily intravenous (IV) Busulfex and fludarabine.

2.2. Secondary Objectives:

2. To record 1 and 2 year overall survival (OS) following transplantation.
3. To record 2 year PFS.
4. To assess non-relapse mortality (NRM) following RTC transplantation at day +100 and 1-year.
5. To assess relapse rate following transplantation at day +100 and 1-year.
6. To assess disease response rate following transplantation at day +100 and at 1-year.
7. To correlate OS, PFS, RR, NRM following HPCT with systemic busulfan exposure.
8. To assess rates of acute and chronic graft-versus-host disease (GVHD).
9. Time to successful neutrophil engraftment.
10. Time to successful platelet engraftment.
11. To assess rates of primary and secondary graft failure.
12. To assess rates of primary and secondary graft rejection.
13. To assess rates of pulmonary toxicity and veno-occlusive disease (VOD) post transplantation, and assess correlation with Busulfex exposure levels.
14. To assess lineage specific chimerism kinetics of donor cells following once daily IV Busulfex based RTC transplantation at days +30, +100, +180 and +365.
15. To correlate chimerism kinetics of donor cells following transplantation with Busulfex exposure levels.
16. To determine immune reconstitution pattern following transplantation at days +30, +100, +180, and +365.
17. To evaluate biologic & genetic markers associated with the malignancy, GVHD and/or the treatment.

3. ELIGIBILITY CRITERIA:

3.1. Inclusion Criteria:

1. Patients aged 18-70 years of age are eligible.
2. Eligible histologies include:
 - B-cell, T-cell or NK-cell NHL refractory to frontline or salvage therapy defined as failure to achieve complete or partial remission according to standard criteria [12].
 - Diffuse large B-cell lymphoma relapsing within 12months of finishing a rituximab containing first line chemotherapy regimen (regardless of response to salvage chemotherapy) or with evidence of c-myc. Primary refractory NHL (regardless of response to salvage chemotherapy).
 - Hodgkin lymphoma which is chemorefractory after at least two prior therapies.
 - NHL in an untreated relapse.
 - Transformed NHL or chronic lymphocytic leukemia undergoing Richter's transformation (regardless of response to chemotherapy).

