Neutrophil engraftment will be defined as first of three consecutive days with ANC $\geq 500 \times 10^9/L$ post-conditioning regimen induced nadir. Similarly platelet engraftment is defined as first day of platelet count $\geq 20,000 \times 10^9/L$, without transfusion for 7 consecutive days. Lineage specific chimerism analysis (CD3 and CD33 subsets), quantitative immunoglobulins and immune reconstitution will be performed on days +30, +100, +180 and +365.

6.4. Veno-occlusive disease:

Veno-occlusive disease (VOD) will be **diagnosed** according to Baltimore criteria (35) as following:

Development of hyperbilirubinemia with serum bilirubin $> 2 \text{ mg/dL}$ within 21 days after transplantation and at least 2 of the following clinical signs and symptoms:

- Hepatomegaly, usually painful
- $> 5\%$ weight gain
- Ascites

For VOD, **severity** will be graded according to the McDonald criteria (36) as following:

- **Mild disease:** If patients showed no apparent adverse effect from liver disease; required no medications for diuresis of excessive fluid or for hepatic pain; and had completely reversible signs, symptoms, and laboratory abnormalities.
- **Moderate disease:** If patients had an adverse effect from liver disease; required sodium restriction and diuretics to minimize signs of fluid excess (edema, ascites, cardiopulmonary congestion) or medication to alleviate pain from hepatomegaly; and eventually showed a complete resolution of all signs of liver damage (a return of weight to baseline, a decrease in liver size, and a decrease in total serum bilirubin to < 34.2 μ mol/L [2 mg/dL]).
- **Severe disease:** If patients showed an effect from liver disease, and signs, symptoms, and laboratory values did not resolve before day 100 or the patient died, whichever occurred first. Death is not a requirement for assignment to the severe VOD category.

6.5. Response Assessment and Criteria:

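### Section 9 plans only mean, SD and 95% CI for continuous laboratory measures, which by inference include donor chimerism (capped at 100%) and immune-cell counts; if most grafts are fully donor or counts are skewed, these summaries can mislead.

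*Combined protocol and SAP*

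**What the plan says.** Section 9 (Statistical Considerations) says that descriptive statistics "will be computed for all correlative laboratory parameters" and spells them out as "means, standard deviations, 95% confidence intervals for continuous variables, and frequencies for discrete data". The list is introduced by "i.e.", so it reads as complete. Neither chimerism nor cell counts are named in that sentence, and the method for the confidence interval is not given.

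The laboratory measures it would cover are set out elsewhere. Section 6.3 states: "Lineage specific chimerism analysis (CD3 and CD33 subsets), quantitative immunoglobulins and immune reconstitution will be performed on days +30, +100, +180 and +365". Note 12 to the calendar in Section 7.1 makes immune reconstitution a number of cells by subset. Section 2.2 includes the objective "To correlate chimerism kinetics of donor cells following transplantation with Busulfex exposure levels", which makes chimerism a correlative measure. Section 1.6 hypothesises that exposure-targeted dosing "will ensure uniform engraftment of donor cells".

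No section plans a median, quartiles, range, log scale, chimerism category or bounded interval for these measures.

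**The concern.** Donor chimerism cannot exceed 100%, and a cell count cannot be negative. If the conditioning works well, many patients may sit at or near 100% donor cells with a few well below. A mean and SD then depend heavily on the few low values, and a symmetric interval can run past the ceiling. If cell counts are right-skewed, the mean lies above what most patients have.

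This would occur with complete data, because it concerns the summary statistic and not who is sampled. Section 9 itself says that "a total of 32 patients limits our ability to perform inferential tests", so these descriptions are likely to be the main output for the chimerism and immune-reconstitution objectives. What is at stake is how clearly a reader can see how many patients reached full donor chimerism and what a typical cell count was.

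**Working it through.** **Inputs.** From Section 9: the summary list, and a ceiling of 32 patients ("We anticipate that a maximum of 32 patients will be accrued to the study"). The plan gives no figure for these summaries, so there is none to reproduce. Assumed here: the shape of the chimerism and count distributions, a Student-t interval, and 20 to 30 patients with data at a given day.

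**Step 1. One worked example.** Take 30 patients at 100% and 2 at 0%.
- Mean = 3000/32 = 93.75%; SD = 24.6.
- t interval: 93.75 ± 2.04 × 24.59/√32 = 84.9% to 102.6%.
- Proportion fully donor: 30/32 = 93.75%, exact (Clopper-Pearson) 95% CI 79.2% to 99.2%, which stays within 0-100%.

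**Step 2. When does the upper limit pass 100%?** Let k of n patients share one value that is d below 100, with the rest at 100.
- Mean = 100 − kd/n.
- SD = d√[k(n − k)/(n(n − 1))].
- The upper limit exceeds 100 when t²(n − k)/(n − 1) > k, whatever the size of d.
- At n = 32, t² = 4.16. For k = 3: 4.16 × 29/31 = 3.89, above 3, so it passes. For k = 4: 4.16 × 28/31 = 3.76, below 4, so it does not.

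So one to three such patients are enough; four are not.

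**Step 3. Coverage for chimerism.** Simulated t intervals, with a share of patients mixed (uniform over the stated range) and the rest at 100%:

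| Mixed share, range | n | Coverage of nominal 95% | Upper limit above 100% |
|---|---|---|---|
| 10%, 0-90% | 20 | 79% | 82% |
| 10%, 0-90% | 30 | 85% | 77% |
| 15%, 0-95% | 20 | 85% | 79% |
| 15%, 0-95% | 30 | 89% | 55% |
| 20%, 40-95% | 20 | 89% | 61% |
| 20%, 40-95% | 30 | 91% | 27% |
| 30%, 40-95% | 20 | 92% | 25% |
| 30%, 40-95% | 30 | 93% | 4% |
| 40%, 40-95% | 20 | 93% | 6% |
| 40%, 40-95% | 30 | 94% | 0.2% |

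For smooth beta-shaped chimerism with no mass at 100%, coverage at n = 32 is 93-94% and the limit is essentially never passed.

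**Step 4. Cell counts, assumed log-normal.** The mean divided by the median is exp(σ²/2). For log-SD σ = 0.8, 1.0 and 1.2 this is 1.38, 1.65 and 2.05, with 66%, 69% and 73% of patients below the mean. Coverage of the nominal 95% interval is 90%, 87% and 83% at n = 20, and 91%, 88% and 85% at n = 30.

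**Step 5. What mean and SD leave out.** 28 patients at 100% and 4 at 50% also give a mean of 93.75%, with SD 16.8. Two complete rejections and four mixed chimeras thus share a mean. The SDs differ (24.6 against 16.8), but neither SD gives the number of patients affected.

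**The case against.** A reader might infer that the planned output cannot tell 32 patients all near 94% from 30 full grafts and 2 complete rejections, and so could give the wrong answer on engraftment. The documents do not support that. The SD is part of the plan, and 24.6 is plainly different from the small SD of a tight group. Rates of primary and secondary graft failure and rejection are separate objectives in Section 2.2, Section 9 plans frequencies for discrete data, and Section 6.3 defines engraftment by neutrophil and platelet recovery. Complete rejections would therefore be counted. This stands.

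It also stands that the pile-up at 100% is an assumption. Section 1.6 speaks of uniform engraftment but gives no chimerism distribution, and with 30-40% of patients mixed the problem shrinks to little. The interval method is unstated, and a bootstrap percentile or suitably transformed interval would respect the bound. Including chimerism and counts is an inference from the word "all", though a strong one, since no other analysis text describes how to summarise them.

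Nor would medians be better on their own. In the Step 1 example the median and both quartiles are 100%, which hides the two failures that the mean and SD show.

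What remains is that the listed statistics never report how many patients have full or mixed chimerism, no chimerism level is defined anywhere, and nothing in the list suits skewed counts.

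**Conclusion.** The point holds as a minor weakness in a descriptive secondary analysis. For chimerism its size depends on how many patients are mixed. At n = 20 to 30, coverage is about 79-91% with 10-20% mixed, and the upper limit passes 100% in 27-82% of samples. With 30-40% mixed, coverage is 92-94%, and passing 100% falls to 6-25% of samples at n = 20 and 0.2-4% at n = 30. For counts, coverage is about 83-91% and the mean is 1.4 to 2.1 times the median.

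These figures rest on an untransformed t interval (a Wald interval has the same symmetric form), on the assumed distributions, and on reading Section 9 as covering these measures. The missing count of patients with full or mixed chimerism depends only on that last reading. The primary endpoint, sample size and stopping rules are unaffected.

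**What to change.** Amend the sentence on laboratory parameters in Section 9.

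- **Chimerism:** add, for CD3 and CD33 at each scheduled day, the number and proportion of patients at or above a pre-specified full-donor level, with an exact 95% CI, plus median, quartiles and range. The investigators should set the level.
- **Cell counts and immunoglobulins:** report median and quartiles, or the geometric mean with a CI computed on the log scale.
- Means and SDs may be kept alongside. If a CI for mean chimerism is kept, name its method.

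The cost is a sentence or two and no new data. The only demand is that the full-donor level be fixed before the results are examined, which also prevents a data-driven choice.
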